1.0 Introduction and Background

Radiation-induced Skin Reactions in Head and Neck Cancer

Radiotherapy (RT) is an effective intervention for treating head and neck cancer. The primary mechanism of action of RT is to create enough DNA damage within each tumor cell to prevent replication and ultimately induce programmed cell death. This mechanism extends beyond the targeted tumor to normal surrounding tissue. This field effect can be visualized by the effect of RT on the skin within a treatment portal. Approximately 85% of patients undergoing RT experience a moderate-to-severe skin reaction (1), the severity of which can be graded using various scales such as the RTOG toxicity criteria (2) and the National Cancer Institute (NCI) Common Terminology Criteria for Adverse Events (CTCAE) version 5 (3). The disturbance of the cutaneous barrier function can significantly impact both health-related quality of life and the course of treatment (4). If the skin reaction is severe enough, a treatment break may be recommended (5). Managing the symptoms associated with skin reactions is important for ensuring completion of RT in a timely manner and increasing patient self-esteem (4). Current skin care recommendations typically include the use of non-fragrant, hypo-allergenic moisturizers (4). Further investigations of topical agents to reduce the symptomatic impact of radiation-induced skin reaction are needed.

KeraStat Cream for Radiation-induced Skin Reactions

KeraStat Cream is a non-sterile, non-implantable, emulsion-based wound dressing intended to act as a protective covering in the management of a variety of minor skin wounds and first and second degree (partial thickness) burns as well as skin undergoing radiation treatment. KeraStat Cream uses human hair-derived keratin proteins and is applied topically to the wound surface to absorb exudate, provide a moist environment, and create an environmental barrier supportive of healing. This cream has recently been studied in the breast cancer patient population undergoing radiotherapy to the breast but has not yet been investigated in patients with head and neck cancer being treated with definitive RT.

All ingredients have been used in FDA-approved products. A biological safety profile has been established for the keratin protein ingredient in KeraStat Cream. Biocompatibility studies were chosen and performed in accordance with ISO 10993-1:2007, "Biological Evaluation of Medical Devices Part 1: Evaluation and Testing." This testing included a full toxicological risk assessment per ISO 10993-17 and 10993-18. KeraStat® Cream has been subjected to a human subject Repeat Insult Patch Test (RIPT) to evaluate the irritation/sensitization potential of the product when applied to uncompromised skin. No adverse skin reactions were observed in 50 subjects evaluated in the RIPT study, and KeraStat Cream was considered a non-primary irritant and non-primary sensitizer to the skin. Additionally, KeraStat® Gel, an FDA-approved hydrogel wound dressing containing the keratin proteins, water, and a preservative, was tested in compromised skin to assess human sensitization study, the Skin Prick Test (SPT). The results of the SPT demonstrated that there was no humoral immune response to keratin and supported pre-clinical testing, which determined that the product would not elicit an immune response.

The current study is considered a nonsignificant risk (NSR) device study according to Food and Drug Administration (FDA) guidance and does not require an Investigational Device Exemption (IDE) in advance of study conduct. NSR device studies must follow the abbreviated requirements presented in 21 CFR 812.2(b) related to labeling, Institutional Review Board (IRB) approval, informed consent, monitoring, records, reports, and prohibition against promotion.

Study Rationale

Although well tolerated by most patients, about 30% of patients undergoing RT develop a Grade 2 or worse early adverse skin reaction (EASR). One study in Taiwan showed 23% of patients undergoing chest wall or whole breast irradiation developed moist desquamation based on the RTOG scale (6). This scale described grade 2 skin toxicity as tender or bright erythema, patchy moist desquamation / moderate erythema; Grade 3 skin toxicity was described as confluent moist desquamation other than skin fold, pitting edema. Both grade 2 and 3 skin toxicities were recorded in the assessment of patients in the Taiwanese study. Another study comparing breast intensity-modulated radiotherapy (IMRT) to conventional tangent fields showed a decrease in moist desquamation, as defined by the NCI CTCAE version 2, from 48% to 31% of patients, suggesting that even with advanced treatment techniques, a significant number of patients experience skin toxicity (7).

Beyond the discomfort patients may experience, EASRs may result in poor patient outcomes. Severe EASRs can require a "treatment break" which, in some cancers, may result in incomplete tumor control and greater chance of local recurrence and lower survival rates. In addition to the potential impact on cancer outcomes, EASRs may affect patients' self-esteem due to the appearance of their skin and recovery time after treatment. Standard skin regimens often include routine application of creams or lotions in an effort to combat the dryness, prevent interruption of the skin's natural barrier (e.g., cracking or flaking), and reduce the appearance of inflammation. Patients often begin using these creams/lotions at the start of RT. Providing patients with a product that moisturizes and reduces the appearance of inflammation may improve patients' satisfaction with their appearance as they progress through RT treatment.

The investigators have demonstrated the feasibility of KeraStat cream during breast RT for patients with breast cancer [data not published]. This study represents a subsequent step to confirm the feasibility of extending comparative studies of KeraStat cream versus routine skin care to patients with a different primary cancer site (head and neck cancer). Due to significant differences in the nature of the head and neck cancer treatment, including the higher risk of high-grade radiation dermatitis experienced by head and neck cancer patients, it is first necessary to confirm the feasibility and tolerability of KeraStat cream in these patients. These data would then directly inform randomized, comparative studies to evaluate the efficacy of KeraStat cream to reduce radiation dermatitis for patients receiving head and neck RT.

KeraNetics has determined that this study is a non-significant risk study under 21 CFR 812.3(m). This device is not intended as an implant. It is not for use supporting or sustaining human life. It is not for a use of substantial importance in diagnosing, curing, mitigating, or treating disease or otherwise preventing impairment of human health, and it does not

otherwise present a serious risk to health, safety, or welfare of a subject. Furthermore, KeraStat® Cream is classified as a wound dressing; wound dressings are classified as nonsignificant risk devices in FDA's "Information Sheet Guidance for IRBs, Clinical Investigators, and Sponsors: Significant Risk and Nonsignificant Risk Medical Device Studies" published January 2006.

2.0 Objectives

This is a single site, randomized, open-label comparison pilot study to assess the feasibility and effectiveness of KeraStat Cream compared with routine skin care (RSC) in managing RT-induced early adverse skin reaction (EASR) in patients undergoing RT to the head and/or neck.

Hypothesis: The use of KeraStat Cream in patients receiving radiotherapy for head and neck is feasible, tolerable, and reduces the severity of EASR in the treated region of interest.

2.1 Primary Objective(s)

To determine the feasibility of the use of KeraStat Cream in patients receiving radiotherapy for head and neck cancer.

2.2 Secondary Objective(s)

- 2.2.1 To determine the tolerability of KeraStat Cream in patients receiving radiotherapy for head and neck cancer compared to routine skin care.
- 2.2.2 To assess the effectiveness of KeraStat Cream in reducing the severity of EASR in patients receiving radiotherapy for head and neck cancer, compared to routine skin care. This will be performed by evaluating:
 - 2.2.2.1 Objective evaluation of EASR using the CTCAE Version 5.0 scale of radiation dermatitis,
 - 2.2.2.2 Patient-reported outcomes of radiation dermatitis using the PRO-CTCAE version 1.0, and
 - 2.2.2.3 Dermatologic-specific quality of life assessment
- 2.2.3 To estimate the amount of KeraStat Cream used per patient and coverage on the skin.

3.0 Patient Selection

3.1 Inclusion Criteria

- 3.1.1 Diagnosis of head and neck cancer planned to receive conventionallyfractionated definitive radiotherapy to the head and neck to a total prescribed dose of at least 60 Gy
- 3.1.2 Able and willing to sign protocol consent form
- 3.1.3 Able and willing to complete tolerability and quality of life assessments
- 3.1.4 Able and willing to have photographs of the affected area taken regularly

3.2 Exclusion Criteria

- 3.2.1 Women who are pregnant, lactating/nursing or plan to become pregnant
- 3.2.2 Previous radiation therapy to the area to be treated with radiation therapy
- 3.2.3 Active, medically necessary use of topical corticosteroids in the irradiation area
- 3.2.4 Active scleroderma or lupus requiring systemic medication
- 3.2.5 Treatment with anti-EGFR antibodies for head and neck cancer (previously or planned)

3.3 Inclusion of Women and Minorities

Men and women of all races and ethnicities who meet the above-described eligibility criteria are eligible to participate in this study. The study consent form will also be provided in Spanish for Spanish-speaking participants.

Based on WFBCCC population estimates, we may expect approximately 20% of participants to be women. Translating this to our sample size estimate of 22 patients, we may enroll approximately 4-5 women. We may enroll approximately 10-13% Black or African American patients. Based on our catchment area and hospital demographics we do not expect high accruals of individuals of Hispanic/Latino, American Indian/Alaska Native or Asian ancestry; however, no individual will be excluded from the study if they satisfy the above inclusion/exclusion criteria. Should we not meet or exceed these estimates, the PI will engage the Office of Cancer Health Equity to discuss strategies to enhance recruitment in these target populations.

4.0 Registration Procedures

All patients entered on any WFBCCC trial, whether treatment, companion, or cancer control trial, **must** be linked to the study in EPIC within 24 hours of Informed Consent. Patients **must** be registered prior to the initiation of treatment.

You must perform the following steps in order to ensure prompt registration of your patient:

- 1. Complete the Eligibility Checklist (Appendix A)
- 2. Complete the Protocol Registration Form (Appendix B)
- 3. Alert the Cancer Center registrar by phone, *and then* send the signed Informed Consent Form, Eligibility Checklist and Protocol Registration Form to the registrar, either by fax or email

Contact Information:

Protocol Registrar [contact]

Protocol Registrar [contact]

Protocol Registrar E-MAIL ([contact])

 Fax/e-mail ALL eligibility source documents with registration. Patients will not be registered without all required supporting documents.

Note: If labs were performed at an outside institution, provide a printout of the results. Ensure that the most recent lab values are sent.

To complete the registration process, the Registrar will:

- assign a patient study number
- randomize the patient
- register the patient on the study

5.0 Study Outcomes and Study Measures

5.1 Primary Outcome

Feasibility of use of KeraStat Cream is measured by patience compliance with directions for use.

5.2 Secondary Outcomes

5.2.1 Tolerability is measured by the number of patients who discontinue skin care regimen due to intolerance for any reason.

^{*}Protocol Registration is open from 8:30 AM - 4:00 PM, Monday-Friday.

- 5.2.2 The effectiveness of KeraStat Cream in reducing EASR will be assessed as follows:
 - 5.2.2.1 Objective assessment of EASR, defined as Grade 2+ using the CTCAE version 5.0 scale of radiation dermatitis (Appendix H)
 - 5.2.2.2 Patient-reported assessment of skin toxicity using the PRO-CTCAE version 1.0 scale of radiation skin reaction (Appendix H)
 - 5.2.2.3 Dermatologic-specific quality of life will be measured using the Dermatology Life Quality Index (Appendix I)
- 5.2.3 Skin coverage by the will be calculated the number of tubes of KeraStat Cream used.

6.0 Treatment Plan

6.1 Study Design

This is a single site, randomized, open-label comparison pilot study to assess the feasibility and effectiveness of KeraStat Cream in managing RT EASR in patients undergoing RT to the head and neck. Sufficient subjects will be screened such that 24 total subjects will complete the study. Patient compliance is expected to be good, so a target recruitment of 28 subjects is anticipated. Patients will be screened for inclusion at their consultation visit in the WFBCCC Department of Radiation Oncology. A total of 28 head and neck cancer patients to receive definitive RT will be recruited and consented.

After informed consent, the patient will be registered to the study and randomized to either routine skin care (RSC) or KeraStat study arms. Patients randomized to the KeraStat arm will be provided with KeraStat Skin Cream for application as often as needed but at least twice daily, morning and evening. Baseline pre-RT assessments will be completed prior to the initiation of RT. These can be completed on the date of RT treatment planning CT simulation scan or later during the radiation treatment-planning process (generally 1.5-2 weeks).

Patients are generally treated with RT using daily fractions delivered Monday through Friday, with weekends and holidays off, for approximately 6-7 weeks. Generally, radiation treatment breaks should be avoided whenever possible, but treatment breaks deemed necessary by the treating radiation oncologist are acceptable and will be recorded, as will the indication for the treatment break. While on treatment, patients are seen by the radiation oncologist (and possibly other support staff including but not limited to nurses, speech language pathologists, dieticians, navigators and case workers) once weekly as part of a routine on-treatment visit. The purpose of this visit is to review the patient's treatment course, monitor for expected and unexpected toxicity, and manage the patient appropriately.

Patients who receive definitive RT receive chemotherapy. Cisplatin is preferred if medically possible, with other cytotoxic regimens acceptable at the discretion of the medical oncologist. Anti-EGFR antibody therapy (i.e. cetuximab) is not permitted.

At weekly on-treatment visits, study evaluations of the skin in the region of interest will occur. These will include objective assessments by study staff, photographs, patient-reported assessments of the skin and a dermatologic-specific quality of life questionnaire. The radiation oncologist will see each patient along with study staff in follow-up 4 weeks after completing RT to assess the patient for RT-induced skin and other toxicities that may have occurred.

6.2 Treatment Administration

Beginning on the first day of RT, patients will be instructed to apply skin care according to their randomization arm (Section 6.2.1). The patient will be instructed to apply the assigned agent every day as needed, but at least twice daily, to the skin of the head and neck within the region of interest.

6.2.1 Randomization

All subjects will be randomized to receive one of two test agents: KeraStat Cream or routine skin care (RSC).

6.2.2 Investigational Agent

KeraStat Cream is a non-sterile, non-implantable, emollient-based wound dressing intended to act as a protective covering in the management of a variety of skin conditions.

6.2.3 Routine Skin Care

Routine skin care will include various standard-of-care, commercially available agents. A list of example agents will be provided to patients in this arm (Appendix J).

6.3 General Concomitant Medication and Supportive Care Guidelines

Concomitant medications are permitted during this study unless otherwise specified in the Exclusion Criteria.

Patients should receive *full supportive care*, including transfusions of blood and blood products, erythropoietin, antibiotics, antiemetics, etc., as clinically indicated. Anti-inflammatory or narcotic analgesics may be offered as needed. Medications considered necessary for the patient's well-being may be given at the discretion of the investigator, i.e., chronic treatments for concomitant medical conditions, as well as agents required for life-threatening medical problems, etc. The reason(s) for treatment, dosage, and dates of treatment should be recorded on the flow sheets.

6.4 Duration of Therapy

Skin care with the assigned agent will be continued until the end of the study period (1 month after end of RT). Study cream will be discontinued if the patient cannot tolerate the agent or if adverse events related to the study agent occur.

6.5 Duration of Follow Up

Patients will be followed for a minimum of 1-month after the completion fo radiotherapy for adverse events monitoring.

6.6 Criteria for Removal from Study

A documented effort must be made to determine why a subject fails to return for the necessary visit or is dropped from the study, and the reason for withdrawal must be recorded in the source documents and case report form (CRF). A subject may withdraw or be removed from the study for any of the following reasons and will be treated as considered appropriate by the Investigator:

- Subject request (for any reason)
- In the opinion of the Investigator, continuation is not in the best interest of the subject
- A serious or unexpected AE occurs such that continuation in the study is inappropriate
- Pregnancy
- RT is stopped

If a subject is prematurely discontinued from participation in the study for any reason, the Investigator must follow up on all ongoing adverse events (if any).

In the event a subject is prematurely discontinued from the study due to an AE, or unexpected AE or serious adverse event (SAE) (as defined in Section 11.5.1), the procedures stated in Sections 11.3-11.9 must be followed.

7.0 Study Assessments

7.1 Study Assessment Visits

7.1.1 Baseline Visit

After informed consent, registration and randomization, study staff will collect baseline demographic information. This includes information such as age, gender, race/ethnicity, medical history, current medications, allergy history. The skin within the region of

interest will be photographed. Study personnel will collect a baseline skin toxicity assessment (Appendix H). Subjects will complete the Dermatology Life Quality Index (Appendix I).

The baseline assessment may occur at any time between registration and the first radiation treatment. A convenient visit may include the radiation treatment planning CT simulation, which occurs in the Department of Radiation Oncology approximately 1.5-2 weeks prior to the start of RT. At this visit, patients may be approached for the baseline assessment. This will be coordinated by study staff.

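### Baseline DLQI, skin form and photographs follow open-label randomisation with no step withholding the arm, and the DLQI analyses do not exclude that baseline

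*Combined protocol and SAP*

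**What the plan says.** Randomisation is part of registration. Among the registrar's closing steps, section 4.0 lists "randomize the patient". Section 7.1.1 then sets the order of the baseline visit: "After informed consent, registration and randomization, study staff will collect baseline demographic information". That sentence names demographics only, but the rest of the paragraph puts the photographs, the Appendix H skin assessment and the DLQI at the same visit. The window is wide: "The baseline assessment may occur at any time between registration and the first radiation treatment". Section 6.1 describes the same sequence.

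The arm is acted on later. Section 6.2 says: "Beginning on the first day of RT, patients will be instructed to apply skin care according to their randomization arm". The patient instructions in Appendix J also start the cream on the first day of radiation.

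Sections 2.0 and 6.1 call the study open-label. In Appendix H the research nurse grades the skin and the treating radiation oncologist confirms the grade; the PRO-CTCAE items and the DLQI are completed by the patient. No masked assessor is named, and no step holds back the arm until baseline is finished.

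Section 11.2.4 compares mean DLQI between arms at every time point in a repeated measures model, and compares each patient's highest score over all time points with a t-test. The calendar in 7.2 schedules a DLQI before RT. Section 11.2.4 does not say whether that score counts.

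**The concern.** A baseline taken once the arm may be known is not protected in the way a pre-randomisation value is. A patient who hopes for one cream, or is disappointed by the other, may answer a self-report questionnaire differently before any cream has been applied. The resulting difference between arms would be neither chance imbalance nor treatment effect.

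The exposure is avoidable, because nothing in the schedule needs the arm before day 1 of RT. Section 6 of the introduction's rationale aside, the order also matters beyond this trial: the study rationale says these data are meant to inform later randomised comparisons, so the visit order may be carried forward. What is at stake here is limited to the two DLQI analyses, since they are the only planned analyses that baseline can enter.

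**Working it through.** **The plan's own figure.** The point has no figure of its own. The one precision figure in the plan, a maximum 95% interval width of 0.578 for compliance with 12 per arm (11.3), reproduces: the Clopper-Pearson interval for 6/12 is 0.2109 to 0.7891, width 0.5781. It depends only on the number of patients and the compliance proportion, so the order of baseline and randomisation does not touch it.

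**Step 1: order of events.**
- Consent, then registration with randomisation (4.0, 6.1).
- Baseline forms and photographs, at any time from registration to the first RT treatment (7.1.1).
- First use of the allocation, on day 1 of RT (6.2, Appendix J).

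Baseline therefore lies between randomisation and first use of the arm. Moving randomisation, or its release, to after baseline would delay nothing that the plan requires earlier.

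**Step 2: which planned analyses can take a baseline score.**

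| Analysis | Section | Baseline score used? |
|---|---|---|
| Compliance, interval per arm | 11.1 | No |
| Discontinuation, interval per arm | 11.2.1 | No |
| Grade 2+ dermatitis, Fisher's exact test | 11.2.2 | No, end of treatment only |
| PRO-CTCAE means | 11.2.3 | No, weekly RT visits and the one-month visit only |
| DLQI, repeated measures | 11.2.4 | Not excluded |
| Highest DLQI, t-test | 11.2.4 | Not excluded |
| Tubes used | 11.2.5 | No |

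No analysis names a baseline covariate or a change from baseline.

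**Step 3: size in the DLQI repeated measures model.** Let T be the number of visits averaged, including baseline:
- 6 weeks of RT: T = 1 + 6 + 1 = 8.
- 7 weeks of RT: T = 1 + 7 + 1 = 9.

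With equal weights, the averaged group contrast is the sum of the T visit contrasts divided by T. If only the baseline contrast moves, by b points, the average moves by b/T. The value of b is not in the documents; the range below is an assumption, on a scale that runs from 0 to 30.

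| Assumed b (points) | b/9 | b/8 |
|---|---|---|
| 1 | 0.11 | 0.13 |
| 2 | 0.22 | 0.25 |
| 3 | 0.33 | 0.38 |

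If the model is instead read as separate contrasts by visit, the full b appears in the baseline contrast and the later contrasts are unchanged.

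**Step 4: the highest-score t-test.** A baseline shift can change a patient's highest score only if the baseline score is that patient's maximum. This should be uncommon in patients about to receive at least 60 Gy (3.1.1).

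**The case against.** The strongest reply is that little in this feasibility pilot depends on baseline, and Step 2 bears that out. The skin grade is hardly exposed: prior RT to the area is an exclusion (3.2.2) and baseline precedes the first fraction, so there is little room for a dermatitis grade other than 0. Later grades, PRO items and DLQI scores are also collected open-label, so correcting baseline leaves that larger route untouched. All of this stands, and it keeps the point a good-practice remark.

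Several stronger readings are tempting and are not supported:

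- *Staff and patients complete baseline knowing the arm.* The documents do not say when the arm is disclosed. They only fail to withhold it.
- *Baseline follows randomisation by up to two weeks.* The 1.5 to 2 weeks in 7.1.1 is the interval from CT simulation to the start of RT. The gap from randomisation to baseline is not given.
- *A baseline-adjusted treatment effect is biased.* No baseline-adjusted or change-score analysis is planned. If one were added later, up to the full b could carry through.
- *Early losses use up the margin of four (28 enrolled less 24 evaluable).* A consented patient who leaves before RT provides no compliance data under either order, so reordering does not restore that margin.

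**Conclusion.** The point holds as a low-priority, nearly free improvement. The order of events is explicit, and there is no provision to keep the arm from those completing baseline. Whether any baseline answer would be affected is a possibility that the documents neither establish nor exclude.

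The consequence is confined to the DLQI analyses in 11.2.4. In an equally weighted average it is about one eighth to one ninth of whatever baseline shift occurs: 0.11 to 0.13 points for an assumed shift of 1 point, and 0.33 to 0.38 for 3 points. This rests on three assumptions: the size of b, that baseline is counted as a time point, and that visits carry equal weight. The primary result and the sample size are unaffected.

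**What to change.** 1. In 4.0, 6.1 and 7.1.1, require Appendix H, Appendix I and the photographs to be completed after consent and before the registrar randomises or releases the allocation. The CT simulation visit, which 7.1.1 already suggests as convenient, would serve. Release the allocation after that and before the first RT day.
2. In 11.2.4, state that the DLQI baseline is a pre-randomisation value and is not a post-treatment time point in the group comparison. Apply this to both the repeated measures model and the highest-score t-test.

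The cost is administrative: the registrar must separate registration from release of the allocation. Registering and numbering the patient first, then releasing the arm once baseline is in, lets the forms carry the patient identifier as they do now. No visit, form or patient is added, and the 28 enrolled, 12 per arm and 0.578 interval width stay as they are.
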